5.5.2 Dispensing the investigational treatment

Each study center will be supplied by Novartis with study drug in packaging of identical appearance. The study drug packaging has a 2-part label. Investigator staff will select the study drug to dispense to the patient using the medication kit number as provided by the IRT system on the label of the study drug kit. Immediately before dispensing study drug to the patient, Investigator staff will detach the outer part of the label from the packaging and affix it to the source document (Drug Label Form) for that patient's unique Patient Number.

After Week 24, once the home study drug administration applies, patients will be expected to perform home drug administrations at the protocol-specified timepoints. For these cases, the Investigator will dispense, supported by IRT, an appropriate number of investigational treatment packages for home administrations and detach the outer part of the label from the packaging as indicated above. The patients will record details including the date of administration at home and will return the used medication and packaging at their next visit to

the study center. Patients will be asked to return all unused medication and packaging at each scheduled study visit.

Study center staff will record in the appropriate documents the dates of the administration.

5.5.3 Handling of study drug

The study drug must be received by designated personnel at the study center, handled and stored safely and properly, and kept in a secured location to which only these designated personnel have access. Upon receipt, all study drugs should be stored according to the instructions specified on the labels. Clinical supplies are to be dispensed only in accordance with the protocol. Technical complaints are to be reported to the respective Novartis Country Pharma Organization Quality Assurance.

The study drug must be stored in a refrigerator from 2 to 8°C (36 to 46°F) with restricted access to designated personnel, and must be carefully controlled in accordance with regulations governing investigational medicinal products and local regulations. The study drug should be protected from the light and must not be frozen.

Medication labels will be in the local language and comply with the legal requirements of each country. They will include storage conditions for the study drug but no information about the patient except for the medication number.

A pharmacist, Investigator or other qualified study center personnel must maintain an accurate record of the shipment and dispensing of study drug in a drug accountability log that will be kept in a secured location to which no blinded site staff (ie, blinded assessor for PASI and IGA mod 2011) would have access to. Monitoring of drug accountability will be performed by a field monitor performing site visits and done at the completion of the study.

At the conclusion of the study, and as appropriate during the course of the study, the Investigator will return all unused study drug, packaging, drug labels, and a copy of the completed drug accountability log to the Novartis monitor or to the Novartis address provided in the Investigator folder at each site.

Patients will be asked to return all unused study drug and packaging at every study visit. A final reconciliation will be done by the site for the last study visit. Details for handling the home study drug administration will be provided separately.

5.5.4 Instructions for prescribing and taking study drug

Secukinumab will be self-administered by patients during the study after the study assessments (including completion of PROs) and scheduled blood samples have been performed.

For Treatment Period 1, all patients will be assigned to the same study drug regimen (300 mg secukinumab s.c. every week for the first 4 weeks, and thereafter every 4 weeks) and will self-administer the study drug at the study site under the supervision and guidance of site personnel at the time-points indicated in Table 5-1. To allow for comparable treatment group data on fixed study visits, patients will be trained for home drug administration prior to Treatment Period 2. If needed, a caregiver can be trained for home administration to provide support to the patient; corresponding training should be documented in the source data at the study center.

For Treatment Period 2, patients will be assigned to 4 different treatment interval groups depending on their PASI response at Week 24. Patients will self-administer their first dose of randomized study drug at Week 24 at the study site under the supervision and guidance of site personnel. Thereafter, patients will self-administer the study drug at either the study site or at home depending on the scheduled study drug administration by study group in Table 5-1 and Table 6-2.

Table 5-1 Timing of study drug administration by study group

_		
	Treatment Period 1	
	(Self-administration at Study Site)	(Self-administration at Home)
All Patients		
All patients	Baseline and	None
	Weeks 1, 2, 3, 4, 8, 12, 16 and 20	
	Treatment	Period 2
	(Self-administration at Study Site)	(Self-administration at Home)
Patients with PASI ≥ 90		
Group 1 (every 4 weeks)	Week 24, 28, 32, 36, 40, 44 and 48	None
Group 2 (every 6 weeks)	Week 24, 36, 48	Week 30, 42
Patients with 75 ≤ PASI < 90		
Group 3 (every 4 weeks)	Week 24, 28, 32, 36, 40, 44 and 48	None
Group 4 (every 2 weeks)	Week 24, 28, 32, 36, 40, 44 and 48	Week 26, 30, 34, 38, 42 and 46

Study drug will be dispensed and self-administered with the support of qualified personnel during office visits in accordance with local laws and regulations or self-administered at home. The blinded assessor for PASI and IGA mod 2011 must not be part of the study drug dispensing or administration process.

The first administration of secukinumab by qualified site personnel will occur at the Baseline visit (Visit 2) after all study scheduled assessments have been performed (and inclusion/exclusion criteria are confirmed) and directly after a blood sample for PK is

collected (pre-dose sample), if applicable. All study drug kits assigned to the patient during the study will be recorded in the IRT.

All dates of injections administered to the patient during the study must be recorded on appropriate eCRF pages for dosage administration.

All injections administered at the study center should be documented in the source documents for drug handling; patient's home administrations should also be documented.

The Investigator should promote compliance by instructing the patient to attend visits and perform home drug administration as planned so the study drug can be administered exactly as prescribed and by stating that compliance is necessary for the patient's safety and the validity of the study. The patient should be instructed to contact the Investigator if he/she is unable for any reason to attend a study visit as scheduled.

5.5.5 Permitted dose adjustments and interruptions of study drug

Treatment interruptions are not permitted. No dose adjustment of study drug is permitted and no interruption of the study drug should be planned during the study.

If a dose of secukinumab was dispensed by the IRT but not administered to a patient, this deviation event must be recorded in the eCRF.

5.5.6 Rescue medication

Use of rescue medication is not permitted during the study.

Patients who do not respond, ie non responders (defined by a PASI < 50 response), or achieve only partial response, ie partial responders (defined by a PASI < 75 response) to the study drug until Week 24 will be withdrawn from the study. This allows for different treatment options outside of the study.

Pooled data from Phase 3 studies shows that 87.6 % of biologic-naïve patients achieved at least the PASI 75 criterion at Week 24 and can therefore be regarded as treatment responders.

5.5.7 Concomitant treatment

All treatments administered during the 6 months prior to start of study drug (including any treatments started during the Screening period) for any reason NOT including psoriasis will be entered in the concomitant medications eCRF or the procedures and significant non-drug therapies eCRF. The start date, end date, dose, unit, frequency, route and reason for administration or change are to be recorded.

In addition, psoriasis treatments used from the time the patient started to treat psoriasis will be reported on the prior psoriasis therapy eCRF. All topical treatments, systemic treatments and phototherapies for psoriasis administered prior to Day 1 (Baseline Visit) will be entered in the prior psoriasis therapy eCRF page (Section 6.2.2).

The Investigator/qualified site staff should instruct the patient to notify the study site about any new medications that he/she takes after being enrolled into the study. All medications, procedures and significant non-drug therapies (including physical therapy and blood transfusions) administered after the patient starts study drug must be listed on the appropriate eCRF page.

Permitted concomitant medications (not for psoriasis or psoriatic arthritis)

Concomitant medications are allowed if not listed in Table 5-2. Dose adjustments of these medications should be avoided during the study. If a dose adjustment of these medications does occur, it must be recorded on the appropriate eCRF page.

Mild to moderate topical corticosteroids (TCS) will be allowed, only if:

- medication was used for an indication other than psoriasis and not on the area affected with psoriasis.
- medication was used for up to 7 consecutive calendar days which includes the first day or less.

Higher than moderate TCS are not allowed from the Week 24 visit (post-dose) to Week 52.

To determine the potency of a TCS regimen, the Investigator/qualified site staff should take into account the potency of the topical steroid, active ingredient, its concentration, base, place of administration, the condition of the patient's skin, and the frequency of administration.

Use of these TCS must be recorded in the eCRF.

There is no restriction on the use of anti-histamines or of corticosteroid drops in the eye or ear during the study.

5.5.7.2 Permitted concomitant medications for psoriasis

After the Screening period, the use of concomitant medication for psoriasis in all body regions is restricted to bland emollients (not supplied by Novartis) and other non-medicated interventions (not listed in Table 5-2). Use of bland emollients must be recorded on the concomitant medications eCRF. Use of any other non-medicated interventions must be recorded in the eCRF.

The definition of bland excludes all topical medications that contain pharmacologically active ingredients such as (but not limited to) lactic acid, salicylic acid, urea, α-hydroxy acids or fruit acids.

Once the patient is screened and if the patient has intolerable scaling and/or itching, the use of bland emollients is permitted. The use of bland emollients should be avoided during the 12 hours preceding a scheduled study visit.

A mild to moderate potency TCS will be allowed for the treatment of the face, scalp, and genitoanal area during the Screening period. These TCS must be stopped the day before Day 1 (Baseline Visit).

Use of these TCS will be recorded on the prior psoriasis therapy eCRF if TCS was used for psoriasis or under Concomitant medications eCRF if TCS was used for any other reason.

5.5.7.3 Permitted concomitant medications for psoriatic arthritis

The use of non-steroidal anti-inflammatory drugs (NSAIDs), analgesic treatments or any other treatment given to treat psoriatic arthritis will be permitted only if not listed in Table 5-2

Use of these medications must be recorded on the appropriate eCRF page.

Dose adjustments of these medications should be avoided during the study. If a dose adjustment of these medications should occur, they must be recorded in the eCRF.

5.5.8 Prohibited Treatment

Use of any treatments displayed in Table 5-2 that could confound the efficacy of secukinumab will NOT be allowed during the study for any indication and washout periods for these treatments are indicated in Table 5-2. If the use of these treatments is required, then the patient must NOT be enrolled into the study. The Investigator/qualified site staff must instruct the patient to notify them about any new treatments he/she takes after the start of the study drug. All prohibited medications and significant non-drug therapies administered after the patient starts study drug must be recorded in the eCRF.

If a prohibited treatment listed in Table 5-2 was used during the study, the patient must discontinue use of the prohibited treatment if he/she wishes to continue in the study. At the discretion of the Investigator/qualified site staff, if the patient's use during the study of a prohibited treatment listed in Table 5-2 presents undue safety risk for the patient, the patient should be discontinued from study drug as per Section 5.5.10. If the patient received a live virus vaccination during the study, the patient must discontinue study drug and complete the end-of-study visit.

Any other protocol deviation that results in a significant risk to the patient's safety will be recorded.

Table 5-2 Prohibited treatment

Prior Therapy (before Baseline Visit [Day 1])

Prior Therapy (before Baseline Visit [Day 1])	
Prohibited treatments ^{†, ‡}	Washout period (before Baseline Visit [Day 1])
Ustekinumab, Guselkinumab	No prior use allowed
Secukinumab	No prior use allowed
Any biologic drug directly targeting IL-17 or the IL-17RA (other than secukinumab)	No prior use allowed
Alefacept, efalizumab	No prior use allowed
Biological immunomodulating agents other than above (eg, etanercept, adalimumab, infliximab)	No prior use allowed
Other new systemic treatments, eg apremilast	No prior use allowed
Any biologic drug against psoriasis or against any other indication	No prior use allowed
Other systemic immunomodulating treatments [§] (eg, methotrexate, cyclosporine A, corticosteroids (oral, i.v., intramuscular, s.c., intra-articular, transdermal) [§] , cyclophosphamide)	4 weeks
Other systemic psoriasis treatments (eg, retinoid, fumarates)	4 weeks
Photo chemotherapy (eg, PUVA)	4 weeks
Phototherapy (eg, UVA, UVB)	2 weeks
Topical treatment that is likely to impact signs and symptoms of psoriasis (eg, vitamin D analogues, pimecrolimus, retinoids, salicylvaseline, salicylic acid, lactic acid, tacrolimus, tar, urea, α -hydroxy or fruit acids)	2 weeks
Live virus vaccinations	6 weeks
Any investigational treatment or participation in any interventional trial	4 weeks or 5 half-lives (whichever is longer)
Prohibited regimen of Topical Corticosteroids (TCS)	
TCS higher than moderate potency on any body location	2 weeks
TCS mild to moderate potency on any body location other than the face, scalp and/or genitoanal area	2 weeks
TCS mild to moderate potency \underline{on} the face, scalp and/or genitoanal area	1 day*

Prior Therapy (before Baseline Visit)	Stable period (before Baseline Visit [Day 1])
Any other treatment known to worsen psoriasis (eg, beta-blockers, calcium channel blockers, lithium)	Stable at least 4 weeks before Baseline Visit (Day 1)

Concomitant therapy (after Baseline Visit [Day 1])

Prohibited regimen of Topical Corticosteroids (TCS)	Prohibited period
TCS any potency	Baseline Visit (Day 1) to Week 24 visit (pre-dose)**
TCS any potency on area affected with psoriasis	Week 24 visit (post-dose) to Week 52 visit
TCS higher than moderate potency	Week 24 visit (post-dose) to Week 52 visit
TCS mild to moderate potency used for more than 7 consecutive days	Week 24 visit (post-dose) to Week 52 visit

[†] If the prohibited treatment was used during the study for any indication, the patient must discontinue use of the prohibited treatment if he/she wishes to continue in the study.

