9.3.1 Prior and concomitant treatment

Prior and concomitant medications will be summarized by treatment group in separate tables.

Prior medications are defined as treatments taken and stopped prior to first dose of study drug. Any medication given at least once between the day of first dose of study drug and the last day of study will be a concomitant medication, including those which were started pre-Baseline and continued into the treatment period.

Medications will be presented in alphabetical order, by anatomical therapeutic classification (ATC) codes and grouped by anatomical main group. Tables will also show the overall number and percentage of patients receiving at least one treatment of a particular ATC code and at least one treatment in a particular anatomical main group.

In addition, significant prior and concomitant non-drug therapies and procedures will be summarized by primary SOC and MedDRA preferred term.

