**Safety set for Maintenance Treatment Period 2 (SAF-TP2)**: The SAF-TP2 includes all patients who were randomized and received at least one dose of study drug at or after the Week 24 visit. Subjects will be analyzed according to treatment received.

Full analysis set for Treatment Period 2 of PASI 90 Responders (FAS-P90R): The FAS-P90R will include all patients who were rated as PASI 90 responders at the Week 24 visit, randomized to treatment groups 1 or 2 and received at least one dose of study drug at or after visit Week 24.

Full analysis set for Treatment Period 2 of PASI 75 Responders who do not achieve a PASI 90 Response (FAS-P75R): The FAS-P75R will include all patients who were rated as PASI 75 responders but do not achieve a PASI 90 response at the Week 24 visit, were randomized to treatment groups 3 or 4 and who received at least one dose of study drug at or after visit Week 24.

**Per-Protocol Set for Treatment Period 2 of PASI 90 Responders (PP-P90R): The PP-P90R** will include all patients from the FAS-P90R who complete the study as scheduled without any major deviations from the protocol which may affect the primary outcome of this study. Major deviations will be based on selected protocol deviations as defined in the Data Review Plan and additional criteria which might have impact on the treatment's efficacy. The final classifications of deviations as major (i.e. leading to withdrawal from the PP-P90R) will be performed in a data review before start of the analysis.

**Follow-Up set (FUS):** all patients from dosing group 3 or 4 who entered the Follow-Up (FU) Period of the study, i.e. who continue into the next phase of the trial at Week 52 and for whom any efficacy or safety data from the FU Period are available.

**Per-Protocol Follow-Up set (PP-FUS):** all patients from the FUS without any major deviations from the protocol in the follow-up period which may affect the rebound assessment at the end of this period. The final classifications of deviations as major (i.e. leading to withdrawal from the PP-FUS) will be performed in a data review before start of the analysis.

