#### 1.7 Prior and concomitant medication

Medications will be identified using Novartis Drug and Therapy Dictionary (NovDTD) including Anatomical Therapeutic Chemical (ATC) code.

Prior and concomitant medications will be summarized in separate tables for all patients in the SAF-TP1 and by treatment group in the FAS-P90R and the FAS-P75R. In the SAF-TP1

concomitant medication will be only displayed for Treatment Period 1, in the FAS-P90R and FAS-P75R only concomitant medication from Treatment Period 2 will be presented.

Prior medications are defined as drugs taken and stopped prior to first dose of study treatment. Any medication given at least once between the day of first dose of study treatment and the last day of Treatment Period 2 will be a **concomitant** medication, including those which were started pre-baseline and continued into the Treatment Period 1. Medication with start date prior to Baseline and without end date will be considered as concomitant medication. Medications starting at the last day of Treatment Period 1 will be considered as concomitant medication for Treatment Period 2. Incomplete start and/or stop dates (e.g. only the year) of medication are supposed to lie before the date of first dose of study treatment.

Medications will be presented in alphabetical order, by ATC codes and grouped by *anatomical main group* (the 1st level of the ATC codes). Tables will show the overall number and percentage of subjects receiving at least one drug of a particular ATC code and at least one drug in a particular anatomical main group.

Specific summaries of prior and/or concomitant medication will be presented for the categories of previous psoriasis therapy presented in Table 1-4.

In addition, medical procedures and significant non-drug therapies as coded in MedDRA will be summarized.

Table 1-4 Categories of previous psoriasis therapy

Level 1 description	Level 1 outcome	Level 2 description	Level 2 outcome
previous	no		
psoriasis	yes	failure**	1
therapy			2
			>=3
			no
			yes

only selected subgroups will be used for reporting

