#### Relapse and Rebound at Week 60

Contingency tables including absolute and relative frequencies will be provided for relapse and rebound at Week 60 in the FUS and in the PP-FUS. Risk differences including 95%-CIs between the (former) dosing groups, i.e. Group 3 vs. Group 4, will also be presented.

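### For Weeks 52 to 60 the protocol contradicts itself on topical corticosteroids, and psoriasis medication taken then has no rule in the FUS relapse and rebound analysis and no concomitant-medication table

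*Protocol*

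**What the plan says.** **Protocol, treatment rules.** In Table 5-2 (5.5.8) the row "TCS any potency on area affected with psoriasis" carries the period "Week 24 visit (post-dose) to Week 52 visit". The rows for higher-than-moderate potency and for mild-to-moderate TCS used beyond 7 days carry the same period. Section 5.5.7 agrees: "Higher than moderate TCS are not allowed from the Week 24 visit (post-dose) to Week 52". Section 5.5.7.2 says "After the Screening period, the use of concomitant medication for psoriasis in all body regions is restricted to bland emollients" (and other non-medicated interventions), with no end date. Section 5.5.6 bars rescue medication during the study. The lead text of 5.5.8 bars Table 5-2 treatments during the study for any indication.

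**Protocol, follow-up.** Under 3.1, Groups 3 and 4 have their last dose at Week 48 and stay off study drug to Week 60, when relapse and rebound are explored.

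**SAP, analysis.** Relapse and the first limb of rebound are defined on PASI (1.8.1.1). Both endpoints are tabulated in the FUS and PP-FUS, and "Risk differences including 95%-CIs between the (former) dosing groups, i.e. Group 3 vs. Group 4, will also be presented" (1.8.8). PP-FUS is "all patients from the FUS without any major deviations from the protocol in the follow-up period which may affect the rebound assessment", with the final classification left to a data review (1.2). Reportable deviations are tabulated by period, including Follow-Up (1.5.1).

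**Concomitant medication.** Protocol 9.3.1 counts use "between the day of first dose of study drug and the last day of study will be a concomitant medication". SAP 1.7 counts "Any medication given at least once between the day of first dose of study treatment and the last day of Treatment Period 2", and shows only Treatment Period 2 use for FAS-P75R.

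**The concern.** The Week 60 comparison is meant to show what happens off drug, including after the every-2-weeks regimen, which protocol 3.3 says had not been tested in maintenance. Patients who flare are the ones most likely to seek treatment. If a treated flare improves before Week 60, the PASI-based rule can miss it. If treatment differs between Groups 3 and 4, the risk difference changes for reasons unrelated to relapse. As planned, no concomitant-medication table would let a reader judge how often this happened.

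**Working it through.** **1. Treatment rules for Weeks 52 to 60, side by side.**

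| Place | Scope | End |
|---|---|---|
| Table 5-2, three Treatment Period 2 TCS rows | TCS | Week 52 visit |
| 5.5.7 | TCS above moderate potency | Week 52 |
| 5.5.7.2 | all psoriasis medication except bland emollients | none stated |
| 5.5.6 | rescue medication | during the study |
| 5.5.8 lead text | all Table 5-2 treatments | during the study |

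SAP 1.2 lists the Follow-Up Period among the study periods, and Week 60 is a scheduled visit, so the first two rows and the last three disagree for 60 − 52 = 8 weeks. The Week 52 end applies to TCS only; systemic treatment, phototherapy and other topicals carry no such end.

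**2. What follows for PP-FUS.** Exclusion requires a major deviation. Whether TCS use after Week 52 is a deviation depends on which row of the table above is followed. The PP-FUS definition also names the rebound assessment only, not relapse.

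**3. Scoring in the FUS.** Neither SAP 1.8.1.1 nor 1.8.8 has a medication clause. By contrast, the three loss-of-response rows of SAP Table 2-1 count psoriasis ConMed as an event, and the time-to-PASI-90 row censors at it.

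**4. Reporting.** The protocol window runs to the last day of study; the SAP window stops at the end of Treatment Period 2. SAP 1.1.1 declares two changes to the protocol's methods, and this is not one of them. Protocol Table 6-1 collects concomitant medication at Week 60, so collected data go untabulated.

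**5. Planned numbers.** Protocol 9.7.1: 1580 × 0.133 = 210.1, so 210 patients, 105 per group. The stated power of more than 90% for about 4% vs 18% reproduces at 0.906 (pooled-variance normal formula), but it concerns PASI 90 at Week 52, not Week 60. No stated figure is in dispute.

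**6. Illustration for relapse.** The documents give no relapse, treatment or recovery rate, so every rate here is assumed. Let r be the untreated relapse rate, t the share of relapsers who treat, and m the share of those who recover past the threshold. Observed rate o = r × (1 − t × m). The 95% CI half-width, with the continuity correction of SAP 2.2.1, is 1.96 × √[o₃(1−o₃)/105 + o₄(1−o₄)/105] + 1/105.

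| r, Group 3 / 4 | t, Group 3 / 4 | m | o, Group 3 / 4 | Difference (points) | Half-width |
|---|---|---|---|---|---|
| 20% / 10% | any | 0 | 20.0 / 10.0 | 10.0 | 10.5 |
| 20% / 10% | 20% / 20% | 0.5 | 18.0 / 9.0 | 9.0 | 10.1 |
| 20% / 10% | 50% / 50% | 0.5 | 15.0 / 7.5 | 7.5 | 9.4 |
| 20% / 10% | 50% / 50% | 1 | 10.0 / 5.0 | 5.0 | 8.0 |
| 20% / 10% | 50% / 20% | 0.5 | 15.0 / 9.0 | 6.0 | 9.7 |
| 20% / 10% | 50% / 20% | 1 | 10.0 / 8.0 | 2.0 | 8.7 |
| 20% / 10% | 20% / 50% | 1 | 16.0 / 5.0 | 11.0 | 9.1 |
| 20% / 20% | 50% / 20% | 1 | 10.0 / 16.0 | −6.0 | 10.0 |

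Equal masking scales the difference by (1 − t × m). Unequal masking can shrink it, enlarge it, or create one where none exists. With larger assumed rates of 30% vs 15%, the unmasked difference is 15 points (2.9 to 27.1). If one third of relapsers in each group treat and recover, it is 10 points (−0.5 to 20.5). If half do in Group 3 and a quarter in Group 4, it is 3.8 points (−6.3 to 13.8).

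**The case against.** - **Psoriasis TCS use in follow-up can be a deviation.** Under 5.5.6, 5.5.7.2 or the lead text of 5.5.8 it could be classed as one, removed from PP-FUS and listed in the Follow-Up deviation table. This stands, but only if the data review reads the protocol that way; Table 5-2 supports the opposite reading. Removing patients who treated a flare also selects on the outcome, so PP-FUS cannot replace a rule in the FUS.
- **Treatment does not erase a relapse automatically.** A treated patient who has still lost more than half of the maximum PASI improvement at Week 60 is scored as relapsed, and rebound has a limb based on new or more inflammatory psoriasis. This stands: misclassification needs both treatment and enough recovery.
- **Low stakes.** SAP Table 1-6 labels both endpoints additional exploratory, with no hypothesis or power claim. This stands and limits the weight of the point.
- **Size is unknown.** The rates are assumed, 105 is the planned randomised number rather than the FUS, and with m = 0 nothing changes. This stands.

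**Conclusion.** The point holds as an internal contradiction in the protocol plus a scoring and reporting gap in the SAP. A flare that is treated and recovers past the threshold *can* be counted as no relapse or no PASI-based rebound in the FUS, and medication started in follow-up appears in no concomitant-medication table.

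Three stronger readings are tempting, and the documents do not support them. A reader might infer from Table 5-2 alone that TCS is unrestricted after Week 52; three other passages say otherwise. A reader might infer that every treated relapse is lost; the PASI rule keeps those still beyond the threshold. A reader might infer that the SAP has no means at all of handling or showing such use; PP-FUS and the deviation table can do so if the use is classed as a deviation.

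No effect size can be derived from the documents. Under the assumptions shown, a true 10-point relapse difference is observed as 2 to 11 points, against a half-width of about 8 to 10.5. The primary and key secondary conclusions are unaffected.

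**What to change.** 1. **SAP 1.7:** restore the protocol 9.3.1 end point (last day of study) and add a Follow-Up Period concomitant-medication table for Groups 3 and 4, with psoriasis medication shown separately.
2. **SAP 1.8.8:** keep the PASI-based relapse and rebound analysis. Add a sensitivity analysis in the FUS in which psoriasis ConMed, as defined in the MAP appendix that Table 2-1 refers to, counts as an event if started after Week 52 and before the Week 60 assessment. It may count patients who start therapy without having lost response, so report it beside the PASI-based result. Do not exclude treated patients from PP-FUS regardless of deviation status, since that selects on the outcome.
3. **Protocol:** reconcile Table 5-2 and 5.5.7 with 5.5.6, 5.5.7.2 and the lead text of 5.5.8 for Weeks 52 to 60. Which rule applies is for the sponsor to decide; the data review needs one answer.

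Cost: SAP wording, one table, one re-run of the relapse and rebound programs, and a protocol clarification. No new data collection is needed.
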